4.3.1.1 Pharmacokinetics and drug metabolism in animals

The absolute bioavailability of olaparib following oral solution dosing to mice, rats and dogs was approximately 60%, 20% and 80%, respectively. Absorption was rapid, exposure increased less than proportionally with dose in mice, more than proportionally with dose in rats and approximately proportionately in dogs. In mice and rats, exposure dropped on multiple dosing. In dogs, little/no change in PK occurred on multiple dosing. Gender differences in exposure were seen in the rat, with female animals having consistently higher circulating concentrations of olaparib than male animals. This gender difference was not seen in the mouse or dog. Plasma

A Phase II, Single-arm Study of Combination Pembrolizumab and Olaparib in the Treatment of Patients with Advanced Cholangiocarcinoma

Version 2.1: 17Mar2023

clearance was low in mice and in dog (1.3-1.7 L/h/kg and 0.39 L/h/kg, respectively) while volume of distribution was low in the mouse and moderate in the dog (<0.5 L/kg and 0.93 L/kg, respectively). These parameters could not be accurately determined in the rat. Olaparib plasma protein binding, *in vitro*, showed some variation between species. Olaparib bound to HSA and α 1AGP although with higher affinity for HSA. Distribution of drug-related material in the rat was rapid and extensive but with little/no distribution seen to the brain, spinal cord or the lens of the eye. In pigmented animals, material was associated with the melanin containing tissues although the association was only transient. In a quantitative whole-body autoradiography analysis of xenograft bearing nude mice, concentrations of radioactivity were higher in the tumor than those in the blood and were cleared more slowly. Metabolism was more extensive in the male rat than in the female rat or in the dog. The majority of the metabolism of olaparib was the result of oxidation and hydroxylation processes with the main site of metabolism being the piperazine carboxycyclopropyl part of the molecule; both the fluorophenyl and phthalazinone ring systems are also subject to metabolism but to a lesser extent. *In vitro*, CYP3A4/5 were shown to be the major isozyme responsible for the metabolism of olaparib. *In vitro*, olaparib was a direct inhibitor of CYP3A and a time dependent inhibitor of CYP3A. Using human hepatocyte cultures, olaparib was able to induce expression of messenger RNA for CYPs 1A2, 2B6 and 3A4. Olaparib was able to inhibit the Phase II metabolism enzyme UGT1A1 but had no appreciable effect against UGT2B7 *in vitro*. *In vitro* studies showed that olaparib was subject to active uptake by isolated human hepatocytes but that it was not a substrate for OATP1B1, OATP1B3 or OCT1 hepatic uptake transporters. Olaparib was a substrate for the efflux transporter MDR1 Pgp, but not for BCRP or MRP-2 efflux transporters. Olaparib was an inhibitor of OATP1B1 and OCT1; it caused no significant inhibition of OATP1B3 and was a very weak inhibitor of NTCP. Olaparib was shown to inhibit MDR1 and very weakly inhibit BCRP. Olaparib did not inhibit MRP-2. Olaparib was able to inhibit OCT2, OAT3, MATE1 and MATE2K. Olaparib had no significant effect on OAT1. Drug-related material was predominantly excreted via the faces in both species.

Pharmacokinetics:

Absorption:

Following oral administration of olaparib via the capsule formulation, absorption is rapid with peak plasma concentrations typically achieved between 1 to 3 hours after dosing. On multiple dosing there is no marked accumulation (accumulation ratio of 1.4- 1.5 for twice daily dosing), with steady state exposure achieved within 3 to 4 days.

Co-administration with a high fat meal slowed the rate (Tmax delayed by 2 hours) of absorption, but did not significantly alter the extent of olaparib absorption (mean AUC increased by approximately 20%). Therefore there is no restriction with diet while olaparib is administered.

Drug interactions:

In vitro, olaparib was an inhibitor of CYP3A4 and an inducer of CYP2B6, but these activities occurred at higher concentrations than are clinically achieved. Olaparib produced little/no

A Phase II, Single-arm Study of Combination Pembrolizumab and Olaparib in the Treatment of Patients with Advanced Cholangiocarcinoma

Version 2.1: 17Mar2023

inhibitions of other CYP isozymes. In vitro studies have shown that olaparib is a substrate of CYP3A4.

Based on the data from a drug-interaction trial (N=57), the AUC and Cmax of Olaparib increased by 2.7- and 1.4-fold, respectively, when Olaparib was administered in combination with itraconazole, a strong CYP3A inhibitor. Simulations using physiologically-based pharmacokinetic (PBPK) models suggests that a moderate CYP3A inhibitor (fluconazole) may increase the AUC and Cmax of Olaparib by 2- and 1.1-fold, respectively.

Based on the data from a drug-interaction trial (N=22), the AUC and Cmax of Olaparib decreased by 87% and 71%, respectively, when Olaparib was administered in combination with rifampicin, a strong CYP3A inducer. Simulations using PBPK models suggested that a moderate CYP3A inducer (efavirenz) might decrease the AUC and Cmax of Olaparib by 50-60% and 20-30%, respectively.

4.3.1.2 Toxicology

In repeat dose oral toxicity studies of up to 6 months duration in rats and dogs, the principal target organ for toxicity was the bone marrow, with associated changes in peripheral hematology parameters, which may be related to the primary pharmacology of olaparib. All changes showed full or partial recovery following withdrawal of olaparib. Olaparib was not mutagenic in an Ames bacterial mutation test, but was clastogenic in a CHO chromosome aberration test in vitro. When dosed orally, olaparib also induced micronuclei in bone marrow of rats. These findings are consistent with genomic instability resulting from the primary pharmacology of olaparib. In reproductive toxicology studies in rats, oral dosing of olaparib prior to mating produced no adverse effects on male fertility. In female rats, although conception rates were unaffected by pre- and peri-conception dosing, embryofetal survival was decreased. Administration of olaparib during organogenesis had an adverse effect on embryofetal survival and also increased major fetal malformations at dose levels that were not maternally toxic. The effects on embryofetal development are considered to be related to the primary pharmacology of olaparib. Exposures in the repeat dose and reproductive toxicology studies were below those achieved at the clinical therapeutic doses of 400 mg daily olaparib (capsule) and 300 mg bid (tablet).

Combination studies in rats suggest potential for olaparib to exacerbate the effects of TMZ and topotecan, although combination of olaparib with these anti-cancer agents did not induce any additional target organ toxicities to those seen with single agent administration.

4.3.2 Clinical experience

The olaparib capsule formulation was registered for use in the EU and US in December 2014.

The recommended olaparib monotherapy capsule dose is 400 mg daily

The Phase III registration studies and most new clinical studies are investigating the tablet formulation, which delivers the therapeutic dose of olaparib in fewer dose units than the capsule.

A Phase II, Single-arm Study of Combination Pembrolizumab and Olaparib in the Treatment of Patients with Advanced Cholangiocarcinoma

Version 2.1: 17Mar2023

The tablet formulation was registered for use in the US in August 2017 for ovarian cancer and in January 2018 for breast cancer. In January 2018, the tablet formulation was also registered for use in Japan for ovarian cancer. The recommended olaparib monotherapy tablet dose under investigation is 300 mg b.i.d.

4.3.2.1 Safety in humans

Monotherapy

Data from the development program indicate that olaparib is generally well tolerated at monotherapy doses up to 400 mg daily (capsule formulation) and 300 mg bid (tablet formulation) in patients with solid tumors. Administration of olaparib monotherapy has been associated with adverse reactions generally of mild or moderate severity (CTCAE Grade 1 or 2) and generally not requiring treatment discontinuation (package insert).

Combination studies

Studies of olaparib in combination with various chemotherapy agents indicate an increase in bone marrow toxicity (anemia, neutropenia, thrombocytopenia) greater than expected if the agents had been administered alone. The effects are generally transient but treatment delays are common and alternative administration schedules/toxicity management processes have been evaluated within some of these studies. When this type of toxicity has occurred it has been managed by routine clinical practice including dose delays, dose reductions, intermittent dosing and/or the use of supportive care measures, including G-CSF.

4.3.2.2 Effect of other drugs on olaparib

CYP3A4/5 are the isozymes predominantly responsible for the metabolic clearance of olaparib. Clinical studies conducted with a tablet formulation to evaluate the impact of known CYP3A inhibitors and inducers have shown that co-administration of a potent CYP3A inhibitor, itraconazole, increased olaparib Cmax by 142% (90% CI: 1.33-1.52) and increased mean AUC by 270% (90% CI: 2.44-2.97) and that co-administration of a potent CYP inducer, rifampicin, decreased Cmax by 71% (treatment ratio: 0.29; 90% CI: 0.24-0.33) and mean AUC by 87% (treatment ratio: 0.13; 90% CI: 0.11-0.16). Moderate inhibitors and inducers of CYP3A are also predicted to significantly alter the exposure of olaparib. It is therefore recommended that known strong CYP3A inhibitors (e.g., itraconazole, telithromycin, clarithromycin, boosted protease inhibitors, indinavir, saquinavir, nelfinavir, boceprevir, telaprevir) or moderate CYP3A inhibitors (ciprofloxacin, erythromycin, diltiazem, fluconazole, verapamil) should not be taken with olaparib.

If there is no suitable alternative concomitant medication then the dose of olaparib or study treatment should be reduced for the period of concomitant administration. With strong CYP3A inhibitors, the dose of olaparib tablet formulation should be reduced from 300 mg bid to 100 mg bid for the duration of concomitant therapy with the strong inhibitor and for 5 half-lives of the concomitant medication after stopping its treatment. With moderate CYP3A inhibitors, the dose of the tablet formulation should be reduced from 300 mg bid to 150 mg bid for the duration of concomitant therapy with the moderate inhibitor and for 3 half-lives of the concomitant medication

A Phase II, Single-arm Study of Combination Pembrolizumab and Olaparib in the Treatment of Patients with Advanced Cholangiocarcinoma

Version 2.1: 17Mar2023

after stopping its treatment. After the washout of the inhibitor is complete, the olaparib dose can be re-escalated.

Strong (e.g., phenobarbital, phenytoin, rifampicin, rifabutin, rifapentine, carbamazepine, nevirapine, enzalutamide and St John's Wort) and moderate CYP3A inducers (e.g., bosentan, efavirenz, modafinil) of CYP3A should not be taken with olaparib. If the use of any strong or moderate CYP3A inducers is considered necessary for the patient's safety and welfare this could diminish the clinical efficacy of olaparib. If a patient requires use of a strong or moderate CYP3A inducer or inhibitor then they must be monitored carefully for any change in efficacy of olaparib or study treatment.

4.3.2.3 Effect of olaparib on other drugs

Olaparib can inhibit CYP3A4 and UGT1A1 in vitro. Using basic models these findings suggest that olaparib has the potential to cause clinically significant interactions with other CYP3A4 and UGT1A1 substrates in the liver or GI tract. However, PBPK modeling predicted olaparib to be a weak CYP3A inhibitor in vivo and did not predict olaparib to be a UGT1A1 inhibitor in vivo. Therefore, caution should be exercised when substrates of CYP3A4 are combined with olaparib, in particular those with a narrow therapeutic margin (e.g., simvastatin, cisapride, cyclosporine, ergot alkaloids, fentanyl, pimozide, sirolimus, tacrolimus and quetiapine). Substrates of UGT1A1 should also be given with caution in combination with olaparib (e.g., irinotecan, nintedanib, ezetimibe, raltegravir or buprenorphine).

Induction of CYP1A2, 2B6 and 3A4 has been shown in vitro with CYP2B6 being most likely to be induced to a clinically relevant extent. It cannot be excluded that olaparib upon co-administration may reduce the exposure to substrates of these metabolic enzymes.

In vitro, olaparib has been shown to be an inhibitor of Pgp, OATP1B1, OCT1, OCT2, OAT3,

MATE1 and MATE2K and is a weak inhibitor of BRCP. Olaparib is predicted by PBPK modeling not to be a Pgp inhibitor in vivo. However, it cannot be excluded that olaparib may modulate the exposure to substrates of OATP1B1 (e.g., bosentan, glibenclamide, repaglinide, statins and valsartan), OCT1 (e.g., metformin), OCT2 (e.g., serum creatinine), OAT3 (furosemide, methotrexate), MATE1 and MATE2K (metformin). In particular, caution should be exercised if olaparib is administered in combination with any statin.

4.3.2.4 The effect of food on exposure to olaparib

The effect of food on olaparib tablet has been investigated. Co-administration with food slowed the rate of absorption (t_{max} delayed by 2.5 hours and C_{max} reduced by 21%), however food did not significantly affect the extent of absorption (AUC), therefore olaparib tablet formulation can be given without regard to food.

A Phase II, Single-arm Study of Combination Pembrolizumab and Olaparib in the Treatment of Patients with Advanced Cholangiocarcinoma

Version 2.1: 17Mar2023

4.4 Overall Rationale

4.4.1 Rationale for the combination of olaparib with pembrolizumab:

Studies reveal a direct causal relationship between cancer and immune dysfunction, whereby tumor cells and their microenvironment are able to evade immune attack by exploiting various immunoregulatory mechanisms in a process termed cancer immunoediting [21]. Regulatory pathways that limit the immune response to cancer are becoming increasingly well characterized and provide new strategies in cancer therapy. Monoclonal antibodies targeting PD-1 that boost the immune system are being developed for the treatment of a number of cancers. On September 4, 2014, the U.S. Food and Drug Administration granted accelerated approval to pembrolizumab (KeytrudaTM, Merck Sharp & Dohme Corp.) for the treatment of patients with unresectable or metastatic melanoma [22]. In May of 2017, the FDA approved pembrolizumab for use in patients who fit these disease criteria and are microsatellite instability-high (MSI-H) or mismatch repair deficient (dMMR). Pembrolizumab is a monoclonal antibody that binds to the PD-1 receptor and blocks its interaction with ligands PD-L1 and PD-L2, thereby releasing PD-1 pathway-mediated inhibition of the immune response, including anti-tumor immune response. The response rate of pembrolizumab in patients with advanced cholangiocarcinoma was 17% in a phase I study [23].

There has been much interest in the combination of PARP inhibitors and immunotherapy, based on preclinical data that support the association of BRCA1/2 mutational status with neoantigen load, tumor infiltrating lymphocytes, and the expression of PD-1/PD-L1 or CTLA-4, thus forming the rationale for combination therapy. There have been data indicating that BRCA1/2 deficient cancers express higher levels of neoantigens and are therefore likely to be more immunogenic. In addition, preclinical studies showed that a combination of PARP inhibition with a CTLA-4 antibody had synergistic activity against BRCA1/2 mutant ovarian cancer [24]. A crosstalk between PARPi and tumor-associated immunosuppression, and provides evidence to support the combination of PARPi and PD-L1 or PD-1 immune checkpoint blockade [25]. PARPi-related upregulation of PD-L1 expression in breast cancer cell lines and animal models appeared to occur via an induction of high GSK3 β Ser9 phosphorylation (the inactive form of GSK3 β). Thus, knocking out GSK3B β activity significantly increased PD-L1 expression. However, PD-L1 expression in GSK3 β -knockout cells was no longer enhanced by PARPi (olaparib) treatment. These results suggested that inactivation of GSK3 β is required for the PARPi-induced PD-L1 upregulation. PARPi attenuated antitumor immunity via upregulation of PD-L1 increased PD-1 binding, which was resistant to activated T-cell killing. Blockade of PD-L1 acted to resensitize PARPi-treated cancer cells to T-cell killing. The data supports the hypothesis that the combination of a PARPi and an immune checkpoint inhibitor is a potential therapeutic approach to cancer treatment.

4.4.1.1 Rationale for the combination of olaparib and pembrolizumab in cholangiocarcinoma:

Research into the molecular pathogenesis of cholangiocarcinoma has revealed potential mechanisms contributing to tumorigenesis. Low expression of excision repair cross complementation group 1 (ERCC1) is found in 74% of cholangiocarcinomas, and this is associated

A Phase II, Single-arm Study of Combination Pembrolizumab and Olaparib in the Treatment of Patients with Advanced Cholangiocarcinoma

Version 2.1: 17Mar2023

with susceptibility to PARP inhibition [26]. In addition, mutations in isocitrate dehydrogenase-1 or -2 (IDH1/2) are found in 25% of cholangiocarcinomas. [27].

It was recently reported that tumors with mutations in isocitrate dehydrogenase-1 or -2 (IDH1/2) proteins exhibit features similar to BRCA-mutant tumors and are more likely to respond better to PARP inhibitors than to IDH inhibitors [28]. IDH is an enzyme that plays a role in the citric acid cycle, the energy-producing unit of the cells, and IDH mutations are found in about 25% of cholangiocarcinomas. The oncometabolites, 2-hydroxyglutarate (2-HG), produced by IDH mutations, induce a state in the cells where DNA repair is profoundly inhibited. This essentially makes them quite similar to breast and ovarian cancers which harbor mutations in key DNA repair genes such as BRCA1 and BRCA2. Furthermore, IDH-mutant patient-derived glioma cells, bone-marrow cultures of IDH-mutant acute myeloid leukemia, and mice bearing IDH-mutant human tumor cells were all susceptible to PARP inhibition [29].

Given the low expression of the ERCC1 protein in the majority of cholangiocarcinomas, together with relative frequent IDH1/2 mutations found in these tumor types, we hypothesize that the combination of PARP inhibition and immune checkpoint blockade will produce a durable anti-tumor response against cholangiocarcinoma by synergistically inducing DNA damage, increasing tumor antigen number and producing durable immune response against cholangiocarcinoma.

4.4.2 Rationale for pembrolizumab dose selection

Support for 200 mg q3w fixed-dose across cancer types:

Because the antitumor effect of pembrolizumab is driven through reactivation of adaptive immune response by blocking PD-1 expressed on T-cells and not direct binding to cancer cells, once the PD-1 on T-cells are fully saturated by pembrolizumab, the shape of the exposure-response relationship across cancer types is expected to be similar [30]. This is supported by exposure-response analysis in multiple indications (Rationale to Change the Dose of Pembrolizumab to a 200-mg Fixed Dose in Various Tumor Indications, 2015). A flat exposure-response relationship was demonstrated between pembrolizumab exposure (or dose) and efficacy or safety within the dose range of 2 to 10 mg/kg or 200 mg to 10 mg/kg (exposure at 2 mg/kg Q3W is similar to exposure at 200 mg Q3W). The similarity in efficacy between the tested dose regimens is further supported by comparisons of ORR/survival outcomes for the tested dose regimens in the melanoma and NSCLC indications. Available PK results in participants with various indications (melanoma, NSCLC, HNSCC, and MSI-H) support a lack of meaningful difference in PK among tumor types [30]. Therefore, the selection of the 200 mg Q3W dosing for pembrolizumab was supported as an appropriate dose for multiple indications, providing exposures which are within the flat therapeutic range of 2 mg/kg Q3W - 10 mg/kg Q2W associated with near maximal efficacy for pembrolizumab and close to the exposure at 2 mg/kg Q3W. On this basis, the approved doses were 2 mg/kg Q3W or 200 mg Q3W in multiple indications.

A Phase II, Single-arm Study of Combination Pembrolizumab and Olaparib in the Treatment of Patients with Advanced Cholangiocarcinoma

Version 2.1: 17Mar2023

4.4.3 The safety of combining pembrolizumab and olaparib

There are ongoing trials of combined PARP inhibitors and immune checkpoint inhibitors. Four trials (NCT02571725, NCT02734004, NCT02953457, and NCT02484404) are assessing the combination of olaparib and durvalumab and/or tremelimumab as salvage treatment of BRCA1 or BRCA2 mutation carriers with recurrent platinum-sensitive or platinum- resistant or refractory epithelial ovarian cancer. One trial (NCT02657889) is evaluating niraparib in combination with pembrolizumab in patients with recurrent, platinum-resistant epithelial ovarian cancer. In addition, in a Study of Pembrolizumab (MK-3475) Combination Therapies in Metastatic Castration-Resistant Prostate Cancer (MK-3475-365/KEYNOTE-365), olaparib at 300 mg bid has been combined with Pembrolizumab (NCT02861573). From the preliminary data from multiple clinical trials, Pembrolizumab at 200 mg every three weeks and Olaparib at 300 mg bid have been well tolerated when the combination of Pembrolizumab and Olaparib have been administered to patients.

In this current phase II study, the dosage of pembrolizumab and olaparib are selected based on the data from the NCT02861573 study. Pembrolizumab will be administered at 200 mg every 3 weeks; olaparib will be administered at a dose of 300 mg by mouth twice per day.

4.5 Rationale for Endpoints

After first-line treatment with a gemcitabine-based regimen, there is no recommended, standard second-line chemotherapy for patients with metastatic gallbladder cancer and cholangiocarcinoma. A multicenter survey and pooled analysis with published data showed that response rates (RRs) to second-line chemotherapy were low (3.4 %), with median PFS and OS of 3.0 months and 6.6 months, respectively [8]. Immune checkpoint inhibitors have shown durable disease control in multiple types of cancer, e.g., melanoma, renal cell carcinoma, non-small cell lung cancer, etc. We propose that an improvement in overall response rate of 35% in patients who receive the combination of pembrolizumab and olaparib after cancer progression or intolerance to frontline treatment (compared to a response rate of 17.5% in patients who received second line systemic chemotherapy per historical control) will be considered clinically meaningful.

A Phase II, Single-arm Study of Combination Pembrolizumab and Olaparib in the Treatment of Patients with Advanced Cholangiocarcinoma

Version 2.1: 17Mar2023

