2.0 TRIAL DESIGN

2.1 Trial Design

We propose an open label, one-arm study to assess the safety and efficacy of olaparib and pembrolizumab in patients with cholangiocarcinoma who have progressed on or cannot tolerate gemcitabine-based therapy.

The primary objective of the study is to assess the ORR of patients with advanced cholangiocarcinoma receiving a combination of pembrolizumab and olaparib. It is hypothesized that the addition of olaparib will improve the response rate of second line systemic therapy from 17.5% to 35% in patients with advanced cholangiocarcinoma.

The study is designed to enroll 33 subjects (for 85% power) with advanced stage cholangiocarcinoma to test the hypothesis that the combination of olaparib and pembrolizumab will increase the ORR in comparison with the ORR from second line systemic chemotherapy (historical control) in this patient population. As our primary study endpoint, which is also being used to determine the sample size of the study, we propose that the combination of olaparib and pembrolizumab will increase the ORR to 35% from 17.5% (achieved with systemic cytotoxic chemotherapy including mFOLFOX—historical control). To allow a 10% patient drop off rate, we expect to enroll a total of 36 subjects into this study. In addition, as secondary study endpoints we expect to see an increase in the PFS and OS of patients receiving combination therapy compared to cytotoxic chemotherapy.

[figure not shown]
A Phase II, Single-arm Study of Combination Pembrolizumab and Olaparib in the Treatment of Patients with Advanced Cholangiocarcinoma
Version 2.1: 17Mar2023

In this study, we propose the collection of three biopsies—one at baseline prior to the start of treatment, one at the beginning of week 4, three weeks after the administration of combination olaparib and pembrolizumab, and one at the time of cancer progression—for the elucidation of exploratory study endpoints. Patients will have a CT or MRI scan at the beginning of treatment and then every 6 weeks thereafter for the first six months of study treatment administration, then every 9 weeks for up to 12 months after the start of treatment, followed by every 12 weeks up to 24 months on study. All patients will continue to receive olaparib and pembrolizumab combination treatment as tolerated unless unacceptable toxicities or cancer progression occur, at which time therapy will cease. In the absence of any problems, the planned study duration is 20-36 months.

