8.1.1.3 Sample Size and Accrual

The primary objective of the study is to assess the ORR of patients with advanced cholangiocarcinoma receiving a combination of pembrolizumab and olaparib. It is hypothesized that the combination of olaparib and pembrolizumab will improve the overall response rate (ORR) from 17.5% (historical control) to 35% in patients with advanced cholangiocarcinoma. The sample size is based on the number of patients that are anticipated to complete the primary objective.

Simon's two-stage Optimum design will be used to test the null hypothesis of $P \leq 0.05$ versus the alternative hypothesis of $P \geq 0.25$. At the first stage, 13 patients will be treated with the combination of olaparib and pembrolizumab. The trial will be terminated if 2 or fewer patients respond. If there are more than 2 responses, the trial will go on to the second stage and 20 more patients will be enrolled to a total of 33 patients. If the total number responding among the 33 patients is ≤ 8 , the null hypothesis will not be rejected and the combination of olaparib plus pembrolizumab will not be investigated further. Using this statistical method, there is a 0.092 (9.2%) probability of erroneously concluding that this drug combination is effective when it actually is not (targeted value of 0.1). If the drug is actually effective, there is a 0.192 probability of concluding that it is not (targeted value of 0.2). The power of the design is 85% with a one-sided significance level of 0.05. If we assume a 10% patient dropout rate, then a total of 36 patients will be needed for the trial.

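### The 17.5% null is called the second-line chemotherapy response rate without a source, while the protocol itself cites 3.4% for that treatment; the only documented rate near 17.5% is pembrolizumab alone at 17%

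*Combined protocol and SAP*

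**What the plan says.** Two sections attach the 17.5% to chemotherapy. Section 2.1 describes it as "17.5% (achieved with systemic cytotoxic chemotherapy including mFOLFOX—historical control"), and says the trial tests whether the combination will "increase the ORR in comparison with the ORR from second line systemic chemotherapy (historical control"). Section 4.5 sets the target of 35% as "compared to a response rate of 17.5% in patients who received second line systemic chemotherapy per historical control". Neither place gives a reference for the number.

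The same paragraph of section 4.5 gives a referenced figure for the same treatment class: "response rates (RRs) to second-line chemotherapy were low (3.4" percent). Section 4.1.1 describes second-line gemcitabine and second-line FOLFOX4, but gives only time to progression, disease-free survival, overall survival and a stable-disease percentage, and no objective response rate.

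For pembrolizumab alone, section 4.4.1 states: "The response rate of pembrolizumab in patients with advanced cholangiocarcinoma was 17% in a phase I study".

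The hypothesis is worded in more than one way. Section 2.1 says: "It is hypothesized that the addition of olaparib will improve the response rate of second line systemic therapy from 17.5% to 35" percent. Section 3.1 speaks of the combination and of second-line systemic therapy. Section 8.1.1.3 says the combination "will improve the overall response rate (ORR) from 17.5% (historical control) to 35% in patients with advanced cholangiocarcinoma", without saying what the historical control received. It then prints a different pair of hypotheses, P ≤ 0.05 versus P ≥ 0.25.

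**The concern.** In a single-arm trial the historical rate is the only control, so its label decides what a result means. Here the label disagrees with the protocol's own cited evidence, and the number sits next to a rate for a different treatment. Two misreadings follow.

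- If the trial fails its rule, the text as written says that the combination did not improve on second-line chemotherapy. A result just below the cut-off would nevertheless be far above the 3.4% that the protocol cites for chemotherapy.
- If the trial passes, the result may be reported as beating chemotherapy and, through the add-on wording in section 2.1, as an effect of olaparib. By the protocol's own figures (17% against 3.4%), pembrolizumab alone could exceed chemotherapy with no contribution from olaparib.

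**Working it through.** **Inputs.** From 8.1.1.3: 13 patients in stage 1, stop if 2 or fewer respond; 20 more to a total of 33; null not rejected if 8 or fewer respond; stated type I error 0.092 and type II error 0.192. Candidate true rates: 3.4% (4.5), 17% (4.4.1), 17.5% and 35% (2.1, 3.1, 4.5, 8.1.1.3), and 5% and 25% (the printed hypotheses in 8.1.1.3).

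**Formulas.** For a true response rate p:

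- P(stop at stage 1) = P(X₁ ≤ 2), with X₁ ~ Bin(13, p)
- P(success) = Σ over x = 3 to 13 of P(X₁ = x) × P(X₂ ≥ 9 − x), with X₂ ~ Bin(20, p)

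**Step 1: reproduce the plan's figures.** At p = 0.175, P(success) = 0.0922, matching the stated 0.092. At p = 0.35, P(success) = 0.8084, so the type II error is 1 − 0.8084 = 0.1916, matching 0.192. A full search for the Simon optimum design at 17.5% versus 35%, with targets 0.10 and 0.20, returns exactly 2/13 and 8/33. The rule was therefore built on 17.5% versus 35%. It was not built on the printed 5% versus 25%, where the same rule has type I error 0.00002 and power 0.391.

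**Step 2: apply the same rule at each documented rate.**

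| True ORR | Where it comes from | P(stop at stage 1) | P(success) |
|---|---|---|---|
| 3.4% | cited second-line chemotherapy | 0.991 | 0.0000009 |
| 17% | cited pembrolizumab alone | 0.615 | 0.080 |
| 17.5% | null, unreferenced | 0.596 | 0.092 |
| 35% | alternative | 0.113 | 0.808 |

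The gap between the two chemotherapy figures is 17.5 / 3.4 = 5.1-fold. The gap to pembrolizumab alone is 17.5 − 17 = 0.5 percentage points.

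**Step 3: look at results either side of the cut-off.** Section 8.2.1 plans an exact 95% interval. Clopper-Pearson limits, taking 33 as fixed, are:

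- 8/33 = 24.2%: 11.1% to 42.3%. The rule is failed, yet the interval lies wholly above 3.4%.
- 9/33 = 27.3%: 13.3% to 45.5%. The rule is passed; the interval excludes 3.4% but includes 17% and 17.5%.
- 11/33 = 33.3%: lower limit 18.0%. This is the smallest count whose interval excludes 17% and 17.5% (at 10/33 the lower limit is 15.6%).

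**The case against.** The strongest reply is that section 2.1 states where the 17.5% belongs: cytotoxic chemotherapy including mFOLFOX. The sponsor may have a source that was simply not cited. Closeness to 17% proves nothing about origin, and the two numbers are not equal. This stands. A reader might infer that 17.5% is really the pembrolizumab-alone rate under the wrong name, and that the trial is tested against the wrong comparator. The documents do not establish that, and to relabel the number outright as a pembrolizumab benchmark would write an unverified origin into the protocol.

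It is also fair that only 2.1 and 4.5 carry the chemotherapy label; 3.1 and 8.1.1.3 do not. The formal hypothesis in 3.1 concerns the combination, and the primary analysis states no conclusion specific to olaparib. The add-on wording is one sentence in 2.1, and even there the reference is second-line systemic therapy.

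Finally, a null above the true chemotherapy rate is conservative. That is correct: at 3.4% a false positive is practically impossible, and at 17% the chance of success, 8.0%, is inside the 10% target.

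None of this removes the conflict inside 4.5, where one treatment class has two rates about five-fold apart, one cited and one not. If a chemotherapy source exists, it has to be given and set against 3.4%.

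**Conclusion.** The point holds as a fault in labelling and sourcing of the null. The 17.5% is presented as a chemotherapy rate without support and against the protocol's own 3.4%. In operation the rule tests against roughly the cited pembrolizumab-alone rate: its success probability is 0.080 at 17%, 0.092 at 17.5%, and below 0.000001 at 3.4%.

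The effect is on interpretation. Missing the rule with 8/33 is not evidence that the combination is no better than chemotherapy at 3.4%. Passing with 9/33 does not exclude 17%. It is tempting to go further and word a pass as a response rate above that expected from pembrolizumab alone. At 9/33 the interval does not support this, and a single arm cannot isolate olaparib at any count. There is no inflation of the type I error, and no case here for changing the sample size or cut-offs.

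The conclusion takes the 3.4% and 17% as printed. The 17% is a phase I figure whose entry in the reference list is titled as interim results, and the protocol gives no sample size or interval for it. It can serve as a reference value but not as a firm benchmark.

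**What to change.** Keep 17.5% versus 35%, the sample size and the 2/13 and 8/33 cut-offs.

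1. In 2.1 and 4.5, stop calling 17.5% the chemotherapy response rate unless a source is cited and reconciled with 3.4%. Without such a source, describe it as a reference threshold close to the cited pembrolizumab-alone rate of 17%, and name 3.4% as the cited chemotherapy rate.
2. Use the same comparator in 3.1 and 8.1.1.3.
3. In 8.2.1, report the ORR and its exact 95% interval against both 3.4% and 17%. State that failing the rule will not be reported as no better than chemotherapy, and that passing it will not be reported as showing a contribution of olaparib.
4. In 8.1.1.3, correct the printed hypotheses (P ≤ 0.05 versus P ≥ 0.25) to those the design uses. The closing statement of 85% power at a one-sided 0.05 level should be corrected at the same time, since the design gives 0.808 power at 0.092.

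The cost is wording in these sections and a somewhat more limited conclusion. No patient, procedure or cut-off changes.
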